## 1. Research background

In recent years, the concept of accelerated rehabilitation surgery (enhanced recovery after surgery, ERAS) has developed vigorously, using a series of optimized evidence-based medical support with preoperative, intraoperative and postoperative programs to reduce postoperative physiological and psychological stress trauma response, so as to achieve the goal of accelerating patient rehabilitation. Perioperative fasting water ban management is an important component of ERAS. Studies have found that prolonged preoperative drinking and fasting will increase the postoperative insulin resistance, cause hypertension, and increase the risk of postoperative infection, which is not conducive to the postoperative recovery of. Oral carbohydrates for at least 2h before anesthesia can reduce the perioperative stress response, improve patient comfort and satisfaction, and promote the postoperative rehabilitation of. The of the Chinese Expert Consensus and Path Management Guide for Accelerated Rehabilitation Surgery (2018 edition) advocates the early postoperative recovery of diet. Studies have shown that the early recovery of oral eating, drinking water and early oral assisted nutrition after elective abdominal surgery can promote the recovery of intestinal motor function, help to maintain intestinal mucosa function, prevent microflora imbalance and displacement, and can reduce the incidence of postoperative infection and shorten the postoperative hospitalization time by. At present, shortening the perioperative water fasting time needs to be concentrated in the preoperative stage. Although the guidelines and a small number of studies recommend the early recovery of diet after surgery, there is no clear stipulation on the recovery time of postoperative diet and drinking water, and most domestic hospitals still perform fasting for at least 6h after surgery.

Carbohydrates are perioperative good oral nutritional fluids. In recent years, studies have shown that preoperative oral carbohydrates can not only supplement the lost

Protocol version: May 17, 2023

water and energy, improve their thirst and hunger, but also improve the postoperative metabolism and stress changes, reduce postoperative insulin resistance, shorten the hospital stay, and accelerate the  recovery of patients compared with clear water. Furthermore, preoperative oral carbohydrate has been confirmed by many studies and does not increase the risk of reflux aspiration in . However, most of the current clinical studies of oral carbohydrate effects on postoperative recovery focus on the preoperative oral phase, and only a few small samples have shown that postoperative oral carbohydrate improves postoperative comfort . Therefore, further systematic studies on the effects of early postoperative oral carbohydrates on postoperative recovery remain lacking.

## **1. Study purpose and study endpoint**

### **1.1 Study Purpose**

**1.1.1 Main study objective:** To evaluate the effect of early postoperative oral carbohydrate on postoperative recovery of the unilateral knee arthroplasty.

**1.1.2 Secondary study objectives:** To evaluate the effect of early oral carbohydrate administration on the comfort and safety of patients undergoing unilateral knee arthroplasty.

### **1.2 Study endpoint**

#### **1.2.1 Primary study endpoints**

Fasting insulin resistance index in venous blood was checked 1d after surgery; (Fasting blood glucose (fasting plasma glucose, FPG) and fasting insulin (fasting insulin, FINS) were measured 1 day after surgery. FPG, detected by oxidase method, FINS detection by radioimmunoassay, using steady state mode assessment to calculate the steady state model insulin resistance index (homeostatic model

assessment for insulin resistance, HOME-IR): FPG (mmol/L) FINS (mU / L) / 22.5.)

## 1.2.2 Secondary study endpoints

### 1.2.2.1 Effectiveness study endpoint

- 1) Fasting insulin resistance index in venous blood was checked on the day of the surgery;
- 2) Fasting insulin resistance index in venous blood was checked 3d after surgery;
- 3) Fasting pre-albumin levels in venous blood on the day of surgery, 1d and 3d after surgery.
- 4) Fasting level of retinol-binding protein in venous blood on the day of surgery, 1d and 3d after surgery;
- 5) The 15-item recovery quality rating scale (QoR-15);
- 6) NRS score of thirst and hunger at 2h, 6h and 8h after surgery;
- 7) Abating distension within 24h after surgery;
- 7) The incidence of hypoxemia and reflux aspiration within 24h after surgery( $SpO_2 <91\%$  under air inhalation was defined as hypoxemia; vomiting associated with severe coughing followed by hypoxemia and lung rales);
- 9) Time of anal exhaust for the first time after surgery;
- 10) The degree of nausea and vomiting;
- 11) Length of hospitalization;
- 12) Postoperative analgesic effect: patients consumed total sufentanil at 48 hours after surgery, number of effective pressure times of the analgesic pump, remediation of analgesia(The salvage analgesic dose was converted to morphine equivalent);
- 13) Postoperative subject satisfaction score.

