Eligible patients were screened before surgery, and an informed consent form was signed. Patients enrolled in the experiment were randomly assigned into one of the three groups. They are early feeding group (EOF 1, EOF 2) and late feeding group (control group). Late feeding group (Group C): Group C patients observed 30min vital signs, returned to the ward to fast and drink for at least 6 h, and gradually drink and eat after anal exhaust. Early drinking water group (EOF 1): EOF 1 group received water in the resuscitation room; early drinking carbohydrate group (EOF 2): EOF 2 group received 200ml 12.5% carbohydrate (100ml containing 12.5g maltodextrin, fructose and glucose) in the resuscitation room.

To evaluate the resuscitation room of patients in the early feeding group: Steward awake score of 6 and awake level 3,5ml / kg lean weight 12.5% carbohydrate or water according to the need of consent. The process of drinking carbohydrates or water is to take 30ml orally first. After observing no abnormal swallowing, the patient was instructed to drink the remaining drinks as needed. After the patient returned to the ward, the liquid diet began to gradually excessive into the normal diet. When the patient was able to tolerate a normal diet, the intravenous fluids were stopped.

Evaluation process of drinking index:

1 ) Steward Score: awake: 0-no response to stimulus; 1-some response to stimulus; 2-full awake.(2) Respiratory tract patency: 0-patient's respiratory tract needs support; 1-patient's respiratory tract can maintain patency without support; 2-patient can cough according to the doctor's guidance.(3) Body mobility: 1 point-the patient has no body activity; 2 points-the unconscious activity of the patient's limb; 3 points-the patient's limb can carry out the conscious activities;

2 ) Grade of sobriety: according to the awake degree of the patient's consciousness: Grade 0: the patient is completely in the sleep state, No response when calling; Level Protocol version: May 17, 2023

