1: The patient is falling asleep, However, head and neck movement, eye opening, or limb movement occurs during breathing; Grade 2: the patient is awake, Have the same performance as level 1, At the same time can also open the mouth, stretch the tongue; Grade 3: the patient is in an awake state, Have the same performance as the level 2, At the same time, they can also clearly tell their own name, age and other information; Grade 4: The patient is awake, Have the same performance as level 3, It can also accurately identify the surrounding environment, And tell you clearly where you are.3.

3 ) The early feeding group (EOF 1 and EOF2 group) did not need to wait for peristalsis. According to the wishes of the patients, the dose was completed within 2 hours after the operation

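### Thirst and hunger are not scored before the study drink, so the comfort endpoint cannot be adjusted for its own starting value

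*Protocol*

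**What the plan says.** Comfort is part of the secondary objective (Protocol 1.1.2), and section 2 expects early carbohydrate to improve it. One direct measure is item 6 of section 1.2.2.1: "NRS score of thirst and hunger at 2h, 6h and 8h after surgery". No section adds an earlier thirst or hunger score, before surgery or before the drink.

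Section 3.1.2 sets the intake rules around these times:

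- Water arm: "EOF 1 group received water in the resuscitation room".
- Carbohydrate arm: "EOF 2 group received 200ml 12.5% carbohydrate" in the same place.
- Both early arms must meet the same awake criteria, take a first 30 ml as a swallowing check, and then drink the rest as they wish. On timing: "According to the wishes of the patients, the dose was completed within 2 hours after the operation".
- Diet in the early arms: "After the patient returned to the ward, the liquid diet began to gradually excessive into the normal diet".
- Late-feeding arm: "Group C patients observed 30min vital signs, returned to the ward to fast and drink for at least 6 h", and then "gradually drink and eat after anal exhaust".

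**The concern.** Thirst and hunger after surgery vary between patients before anyone drinks. Patients may differ in how thirsty they already are when they reach the resuscitation room. With the first score at 2 h, that variation stays in the error term of every comparison, and a reader cannot see whether the arms started alike.

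The gap lies in data collection. The choice of covariate can be left to an analysis plan, but the score has to be taken at the bedside before the first mouthful.

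The same timetable raises a question of interpretation. At 2 h and 6 h the early arms may already be drinking, and once on the ward taking a liquid diet, while Group C is still held to its fast. A lower score in EOF 2 than in Group C therefore reflects the whole early-intake strategy. At stake is how sharply, and how correctly, the trial can speak on comfort.

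**Working it through.** The protocol gives no figure for this endpoint (no standard deviation, correlation or power), so there is nothing to reproduce. The check is a timeline followed by a precision calculation.

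**1. Scores against the drink.** Scores fall at 2, 6 and 8 h (1.2.2.1, item 6). The drinking deadline is 2 h (3.1.2, item 3 of the drinking evaluation). Lag to the first score = 2 h minus the finishing time. For illustrative finishing times:

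- 0.5 h: 2 − 0.5 = 1.5 h
- 1.0 h: 2 − 1.0 = 1.0 h
- 1.5 h: 2 − 1.5 = 0.5 h
- 2.0 h: 2 − 2.0 = 0 h

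Every compliant patient is scored at or after finishing, and none before starting.

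**2. Scores against Group C's fast.** Earliest end = start of the clock + 6 h.

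- Clock from the end of surgery: 0 + 6 = 6.0 h
- Clock from return to the ward after 30 min of observation (taken to begin at the end of surgery): 0.5 + 6 = 6.5 h

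The 2 h score lies inside the fast on both readings. The 6 h score lies on the boundary on the first reading and inside the fast on the second. The 8 h score comes after the earliest end, but intake also waits for flatus, so some patients may still be fasting.

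**3. What each contrast holds constant.**

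- EOF 2 versus EOF 1: same place, awake criteria, drinking procedure, 2 h window and later diet. The type of drink differs.
- EOF 1 or EOF 2 versus Group C: the drink, permission to take fluids and the ward diet all differ.

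**4. Value of a pre-drink score.** With the score as a covariate, the variance of a between-arm difference is multiplied by about 1 − r², where r is the correlation between the pre-drink and later scores. The values of r are assumed.

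- r = 0.3: r² = 0.09, factor 0.91, standard error × √0.91 = 0.95
- r = 0.5: r² = 0.25, factor 0.75, standard error × √0.75 = 0.87
- r = 0.6: r² = 0.36, factor 0.64, standard error × √0.64 = 0.80

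The gain is probably largest at 2 h and smaller later, since intervening intake should weaken the correlation. That is a judgement; the protocol has no data on it.

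**The case against.** The strongest objection is that the design already answers the main question. Allocation is random, so comparing the arms on later scores alone is unbiased. Early intake against fasting is the contrast the trial intends: section 3.1.2 names early and late feeding groups, and the research background gives fasting of at least 6 h as usual domestic practice. This is also one of 13 listed secondary effectiveness items. All of that stands, and it limits the point to precision and labelling.

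A reader might infer more, but the protocol does not support it:

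- *The schedule cannot isolate the effect of carbohydrate.* It can: EOF 2 versus EOF 1 does so at all three times, and Group C's fast plays no part.
- *The missing score biases the comparison because thirstier patients drink more.* The amount drunk is behaviour after randomisation, within the assigned arm. It does not confound a comparison by arm.
- *The variable lag before the 2 h score invalidates it.* The same window applies to both early arms. Lag may blur an early effect but favours neither arm. Rescoring at a fixed interval after the drink would give up a simple common schedule and has no natural counterpart in Group C.
- *The 6 h score always falls strictly inside Group C's fast.* That holds only if the 6 h run from return to the ward. On either reading, no Group C patient may drink before that score is due.
- *The trial will credit a difference from Group C to carbohydrate.* No section says so.

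Covariate choice and the naming of contrasts are commonly left to an analysis plan. That does not remove the point, because no such plan can supply a score that was not taken.

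**Conclusion.** The point holds as a modest, inexpensive improvement to a secondary endpoint. Without a pre-drink thirst and hunger score, the trial gives up about 9% to 36% of the outcome variance that adjustment could remove, if the correlation is 0.3 to 0.6, and it loses a check of balance at the start. The validity of the randomised comparisons is not in question.

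Contrasts with Group C at 2 h, and up to at least 6.0 or 6.5 h depending on the clock, compare early intake with fasting and should be described that way. A comfort claim specific to carbohydrate has a sound basis in EOF 2 versus EOF 1.

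That last statement assumes both early arms follow the same volume rule. Section 3.1.2 gives a lean-weight amount for carbohydrate or water, but also a fixed volume for EOF 2 alone, and these passages must be reconciled.

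**What to change.** In section 1.2.2.1, item 6, add one thirst and one hunger NRS in all three arms at a common point in the resuscitation room before any intake; in EOF 1 and EOF 2 this means before the first 30 ml. The point should be defined identically in every arm. If early-arm patients were scored systematically sooner or later than Group C, the covariate itself would differ by arm.

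Use that score as a covariate in the analysis of the 2, 6 and 8 h scores, and keep those three times. Add a sentence that contrasts with Group C are reported as early intake versus fasting, and that any carbohydrate-specific comfort claim rests on EOF 2 versus EOF 1.

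The cost is two short questions and two more case report form fields per patient, asked while patients are already being assessed or observed. No dose, fasting rule or other clinical step changes.

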### 1.2.2.2. Safety study endpoint

- 1) The incidence and severity of various adverse events (AE) from the start of oral carbohydrates to the end of the trial;
- 2) The incidence and severity of adverse events such as nausea, vomiting and hypoxemia from the first start of drug administration to the end of the trial;
- 3) Number of antiemetic drugs used within 24h after the first start to drug administration;

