##### 4.2 Exclusion criteria:

- Preoperative existence of gastric emptying disorders, such as gastrointestinal obstruction, gastroesophageal reflux, or previous gastrointestinal surgery;
- Patients with diabetes mellitus, severe renal dysfunction, or other severe metabolic diseases;
- History of motion sickness;
- Mental disorder, alcoholism, or a history of substance abuse;
- Patients with abnormal swallowing function;
- The operation time is greater than 3 hours;
- Maltodextrin fructose allergy or intolerance;

4.2 Standards for dropout cases: signed the informed consent form and screened the Protocol version: May 17, 2023

qualified withdrawal cases in the pre-intervention, during the intervention and after the intervention follow-up process after entering the study.

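### The only case definition of reflux aspiration requires vomiting first, so aspiration on drinking or after regurgitation without vomiting is not counted as aspiration

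*Protocol*

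**What the plan says.** Among the secondary effectiveness endpoints, Protocol section 1.2.2.1 has one item for "The incidence of hypoxemia and reflux aspiration within 24h after surgery". A single bracket then explains both terms. An SpO2 below 91% "under air inhalation was defined as hypoxemia". The second clause, "vomiting associated with severe coughing followed by hypoxemia and lung rales", describes reflux aspiration. The protocol gives no other case definition of aspiration.

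Other sections show that the protocol has swallowing and aspiration in mind:

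- Section 3.1.2 has early-feeding patients take 30 ml first. "After observing no abnormal swallowing, the patient was instructed to drink the remaining drinks as needed".
- Section 4.2 excludes "Patients with abnormal swallowing function".
- The research background states that preoperative oral carbohydrate "does not increase the risk of reflux aspiration". That statement does not cover postoperative intake.

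The safety endpoints in section 1.2.2.2 cover "The incidence and severity of various adverse events (AE) from the start of oral carbohydrates to the end of the trial" and "adverse events such as nausea, vomiting and hypoxemia from the first start of drug administration". Aspiration is not named in either.

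**The concern.** The intervention is a drink given in the resuscitation room soon after surgery. It adds a route to aspiration: the drink going the wrong way on swallowing, or coming back up without vomiting. The case definition starts from vomiting, so it leaves this route out even when coughing, hypoxemia and rales are all present.

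Safety is a stated secondary objective (section 1.1.2), and this is the only endpoint that names aspiration. If the route that the drink adds is outside the definition, a low or equal aspiration count says less about the safety of early drinking than it appears to. The definition also governs what staff record at the bedside. If cough on drinking or regurgitation is not captured there, later analysis cannot recover it.

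**Working it through.** No arithmetic applies. The protocol states no aspiration rate, sample size or margin for this endpoint, so there is no figure to reproduce. The check is a literal reading of the definition, followed by a search for any other route by which the event would be counted.

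**Step 1: the logic of the definition.** The elements are vomiting, severe coughing, hypoxemia (SpO2 <91% on air) and lung rales. They are joined by words of association, sequence and conjunction, with no alternative offered. All four are needed, and vomiting comes first.

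**Step 2: apply it to plausible events within 24 h.**

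| Event | Counted as reflux aspiration? | Counted as hypoxemia in the same item? |
|---|---|---|
| Vomiting, severe cough, SpO2 <91% on air, rales | Yes | Yes |
| Cough on the drink, no vomiting, SpO2 <91% on air, rales | No | Yes |
| Regurgitation without vomiting, cough, SpO2 <91% on air, rales | No | Yes |
| Vomiting, severe cough, rales, oxygen started before any reading on air | No | No |

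**Step 3: do the other routes repair the gap?** The hypoxemia count picks up rows two and three, but it mixes them with desaturation from any other cause, and every patient has a sufentanil pump (section 3.1.2). The adverse event endpoints could record a recognised aspiration, but they do not name it. Their clocks start at oral carbohydrates or at drug administration. Group C has neither as an assigned intervention, and the water group fits only by extension. Neither route yields an aspiration count on a common footing across the three groups.

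**Step 4: is the gap even across groups?** Under section 3.1.2, EOF 1 and EOF 2 drink in the resuscitation room, complete the dose within 2 hours after the operation, and start a liquid diet on return to the ward. Group C takes nothing by mouth for at least 6 h after returning to the ward. In those first hours, aspiration on a postoperative drink can arise only in EOF 1 and EOF 2. Later in the 24 h window Group C may also drink, and regurgitation can occur in any group at any time. The omitted events are therefore likely, but not certain, to fall more often in the early-drinking groups.

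**The case against.** The strongest case on the other side has five parts.

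- **The events are not lost.** A reader might infer that they go entirely uncounted. The documents do not support that: a patient with SpO2 <91% on air is a hypoxemia case in the same item, and section 1.2.2.2 covers adverse events in general. This stands. The gap is in the aspiration count alone.
- **The omitted events are not confined to the early-drinking groups.** A reader might infer that only those groups can have them. Regurgitation needs no postoperative drink, all patients take 200 ml before surgery, and Group C may drink within 24 h. This stands, so the direction of any bias is a possibility and not a certainty.
- **The expected safety result rests on another endpoint.** Section 2 expects no increase in adverse events, which section 1.2.2.2 measures without this definition. This stands as a limit on the consequence. It does not mend the one endpoint that names aspiration.
- **The label and the translation.** Choking on a swallow is not strictly reflux, and the bracket is rough translated text that never says outright that it defines reflux aspiration. This stands in part. The parallel with the hypoxemia clause leaves no other sensible reading, and regurgitation without vomiting falls within the ordinary meaning of reflux.
- **A broad definition has its own bias.** A fasting control makes allocation evident, and early drinkers are watched while swallowing. Accepting hypoxemia or rales alone, or any start of oxygen, would admit discretionary events that closer observation could inflate in EOF 1 and EOF 2. This stands, and it is why the fix keeps both objective signs.

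**Conclusion.** The point holds in a limited form. The protocol's only case definition of reflux aspiration makes vomiting necessary, so aspiration on swallowing the drink or after regurgitation without vomiting is not counted as aspiration, even with coughing, hypoxemia and rales. The hypoxemia count and the adverse event endpoints may catch such an event, but neither separates aspiration clearly by group. Because the early drink falls in EOF 1 and EOF 2 while Group C fasts, the omission may favour a finding of no added aspiration.

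The size cannot be stated. A reader might want to put a percentage on the missed events, but the protocol gives neither the share of aspirations without vomiting nor the frequency of early oxygen, so any figure would rest on invented inputs.

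The conclusion assumes that the second clause of the bracket is the aspiration definition and that its connecting words mean what they say.

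**What to change.** For endpoint counting only, with no change to patient care, restate the aspiration event in section 1.2.2.1 as follows:

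- **Trigger:** coughing or respiratory distress after vomiting, regurgitation or drinking.
- **Required signs:** followed by both SpO2 <91% on air and new lung rales.
- **Window:** the same 24 h after surgery in all three groups.
- **Subset:** report events meeting the present vomiting-based definition separately.
- **Sensitivity count:** record separately the events in which oxygen was started before an air reading was taken.

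The cost is one rewritten definition and a few case report form boxes (trigger, and oxygen before an air reading), with no added test. There is a small downside. A few more non-specific events will be admitted, and closer observation of the early-drinking groups could raise their count somewhat. Requiring both objective signs and reporting the strict subset alongside limit this.
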